The control group is designed to control for the daily use of a telehealth program (an attention control) as well to equate basic information about urinary incontinence between groups. The control program matches the number of interactions but is limited to general prostate cancer information; perioperative care; wetness, odor and skin care management but no content on pelvic floor muscle training and bladder control strategies. Outcome measures will be administered by the telehealth program in both groups. For the Health Buddy, data are stored on the telehealth program and transmitted each night via toll-free telephone lines to a database behind a secure VA firewall as they are in the CCHT program. This was proven to be feasible and practical in our pilot study. For the web-based program, the data will be stored on a secure website with VA-approved encryption. Both groups will have use of the telehealth program monitored and quantitated. Preoperatively and 2 months postoperatively, telehealth sessions will be daily. After 2 months postoperatively, both groups will log-in weekly for outcomes measurement until 6 months postoperatively and two more times at 9 & 12 months postoperatively. If we cannot obtain a response through the telehealth program, the questionnaires will be mailed to the participants along with a postage-paid return envelope. These measures are delineated in detail in the Outcome Measures section and in Table 5. The telehealth content for each session for both groups ends with a "fun fact" including sports and other trivia, famous men who have done well after prostate cancer diagnosis, etc. which have been successfully implemented in the pilot study and promoted adherence to the daily home telehealth program, in our pilot study as well as in the CCHT programs VA wide. At 12 months, Veterans still incontinent in both groups will be offered treatment in the GRECC Continence Clinics or the VA Urology Clinic.

THEORETICAL FOUNDATION

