The study coordinators at each site will attend all VA urology clinic sessions in which men could be scheduled for radical prostatectomy. In our pilot study, we have found that having a recruiter in clinic is essential for optimal enrollment, as busy urologists forget to call us to enroll patients. The study will be introduced to patients scheduled for radical prostatectomy by the urologist, and then the study coordinator will obtain informed consent from willing patients. Consenting participants will then complete the brief baseline assessment in clinic. Access to the telehealth program will be given to the participant after a brief training session. Our pilot study has shown that participants who were mailed a telehealth device had no trouble setting it up. The simple set-up instructions are very clear and have been performed successfully by hundreds of Veterans and their families across the U.S. If they prefer, participants can return for a separate appointment to complete baseline assessment.

Our goal will be to enroll as many participants in person as possible. However, the study coordinator will check the surgery schedule weekly, and if a patient appears on the surgery schedule for radical prostatectomy and has not been enrolled in the study, the patient will be telephoned by Urology Clinic staff and if interested, then contacted by study staff. They will be invited to come in for an enrollment visit. As a back-up, or if the patient prefers, the study can be explained by telephone, a consent form mailed to the patient, any questions answered by telephone, and the consent form signed and mailed back. Once the consent form is returned, the baseline data can be completed by telephone, and when complete data has been received, the patient will be sent his telehealth program access.

If participants are enrolled more than 28 days before their surgery date, they will not begin the program until 28 days before surgery. As in the inclusion/exclusion criteria section, if a participant cannot start the telehealth program at least 7 days before surgery, he will be excluded. He and the urologist could decide to delay his surgery so that he could participate if the participant desires. This would not affect his prostate cancer

outcome and might improve his continence outcome. Every effort will be made to enroll participants at least 14 days before their surgery.

Recruitment Procedures at the University Affiliate Urology Clinics

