Birmingham site - Patients who are planning to undergo a prostatectomy at UAB will be informed of the study by their urologist at their pre-operative appointment at The Kirklin Clinic. The urologist will put a sentence in his clinic note that the patient has been informed about the study and agreed to have a study coordinator call him with more information. The urology nursing staff will email the study coordinator (secure UAB email to secure UAB email) with the names, MR numbers, and phone numbers of all patients who agree to be called. We will not be conducting any study procedures in The Kirklin Clinic. Our study coordinator will call the patient and explain the study to him. If he agrees to participate, she will conduct an informed consent discussion, answer all the patient's questions and mail the VA consent form, the VA HIPAA and the UAB HIPAA form - Authorization for Use/Disclosure of Health Information for Research form. Should the patient wish to meet in person rather than do a telephone consent, we will meet with them at the TKC Urology Clinic during an already scheduled appointment or at the BVAMC (whatever the patient prefers). If the patient has questions once he receives the consent form in the mail, he can call and have a second discussion with the study coordinator and/or arrange an in-person visit. Should the patient request an in-person visit and provide us with a signed consent form at that visit, we will transport the consent form in a locked bag from The Kirklin Clinic to the Birmingham VAMC.

Philadelphia and Atlanta sites – Recruitment at the Affiliate Urology Clinics at Philadelphia and Atlanta will be developed by the site and approved by their VA and University IRBs as appropriate with local regulations.

Stratification and Randomization

In order to assure between-group comparability, subjects will be stratified on two dimensions with possibility of impacting outcome:

1. Age (<65 years and 65 or older) – older men are more likely to have post-operative incontinence.

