2. Gleason Score (<7 and 7 or greater) - named after Donald Gleason, a pathologist at the Minneapolis VAMC who developed this important tool with other colleagues in the 1960s, to classify the differentiation of the cancer cells in the prostate biopsy; the higher the score, the more anaplastic the tumor pattern, and the more likely that the tumor has spread beyond the prostate. The Gleason score serves as an indication of the likely extent of prostate cancer and serves as a surrogate for the surgical margins that will be necessary to resect the cancer, which will occur after randomization. The more extensive the resections are associated with worse continence outcomes, contingent particularly on whether one or both neurovascular bundles could be preserved. *Seven is considered the cut point for higher risk disease.*

Within each stratum, blocked randomization will be performed using a variable block size and a table of random numbers to avoid inequity in the total number of subjects assigned to each group. Stratification will be used *only* to ensure that the treatment groups are similar on severity and treatment factors, not to compare groups. Each site will have a separate randomization schedule to avoid unequal distributions between sites. Also, blocking is used not to create comparison groups but only to ensure that the groups are similar in size.

Intervention

This telehealth technology allows for daily guidance via a series of interactive screens. At the time of his choosing each day, the participant interacts with a 10-minute session. Informational screens are interspersed with screens that pose questions. Some questions are on understanding of a technique, some on adherence to the rehabilitation program. Depending on the participant's answers, the telehealth program's branching logic permits different paths. For example, if the participant answers that he has not yet resumed his exercises postoperatively, the next screen will inquire about the reason. Four common reasons are listed, and appropriate information and instructions are provided depending on his endorsement of a reason. Some responses, such as repeated failure to resume exercises postoperatively, a lapse in adherence to exercises preoperatively once adherence is established, failure to master a specific skill such as urgency suppression, or

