up or down depending on the error rate detected. Manual inspection of the forms will be done to resolve differences in the dually entered data. The principal investigator and statistician will meet with the database manager to review accrual, data entry, and examine the database for outliers or data base entry errors monthly.

Data Analysis

Preliminary Analyses

Although subjects will be stratified and randomized, the equivalency of the two groups will be evaluated on selected variables that might influence treatment outcome: study site, age, nerve sparing surgery, body mass index. The chi square statistic will be used for the categorical variables and the two-sample t test for continuous variables. Normality will be carefully assessed for continuous outcomes and if the assumption is violated, non-parametric methods will be used.

Outcome Variables Analysis

Primary outcome analysis: duration of incontinence (time to achieve continence after surgery). Participants will be considered continent if they answer that they leak urine “never” on the ICIQ-SF for 3 weeks in a row. Please see Methodology section for complete explanation of this measure. Baseline time for this measure will be the day of surgery. Median time until continence and its 95% confidence interval will be calculated per group. The duration of incontinence will be examined using the Kaplan-Meier procedure, in which all protocol eligible participants are analyzed. Men who did not have a prostatectomy – either due to positive lymph nodes during surgery or because they changed their mind and selected another treatment after randomization but before surgery will not be included in the analysis. All other men randomized will be included. The duration of incontinence will be compared between the 2 groups using the log rank test. We will also compare continence rates at 9 and 12 months.

Secondary outcome analyses (severity of incontinence, impact on quality of life, and patient reported evaluations of improvement and satisfaction with treatment) will be measured by:

1. ICIQ-SF total score
2. EPIC-UI total score
3. Pad use from the EPIC-UI
4. Patient estimation of improvement measured by the GPI and EPI
5. Patient satisfaction as measured by the PSQ
6. IIQ – total and subscale scores
7. IPSS Quality of Life Question (IPSS QoL)
8. Questions on activity restriction, amount of disturbance caused by incontinence
9. Return to work or normal activities after surgery.

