Our hypothesis for the secondary outcomes is that total ICIQ-SF, EPIC-UI total Score, Pad use, GPI, EPI, PSQ, IIQ, IPSS QoL, return to work or normal activity, and amount of disturbance caused by incontinence will be better in the pelvic floor muscle rehabilitation group.

Initially, descriptive analyses will be conducted to examine distributions of the frequency of symptoms and possible covariates. Extreme values will be checked for accuracy and recoded as indicated. Transformations may be employed to correct for skewness or heterogeneity as needed.

The ICIQ-SF total score and the EPIC-UI total score will be analyzed using multiple regression analysis to regress the 6 and 12-month scores on treatment group, while controlling for baseline score (first score after catheter removal post-operatively). Pad use will be dichotomized into no pad use and any pad use. Pad use will also be analyzed descriptively as no pads, 1 pad, or 2 or more pads. The chi square statistic and the t test for independent samples will be used. Both measures are necessary for comparison with earlier studies. Multiple regression will be used for the GPI, EPI, and PSQ at 6 and 12 months. There is no baseline for these measures as they are the patients’ evaluations of their improvement and treatment satisfaction. For the IPSS QoL question, questions on activity restriction, disturbance, and return to work or normal activity, the chi square statistic and the t test for independent samples will be used.

Qualitative Analysis

To ensure analytic rigor, the following procedures will be followed: (1) data immersion (reading/listening and re-reading/listening to the text); (2) thematic identification and articulation (discovering, naming, defining codes/variables); (3) data categorization (developing a coding scheme); (4) pattern articulation (identifying connections within and between codes); (5) data interpretation (recognizing how the patterns transcend individual experiences and reflect larger social processes). As an analytical process, content analysis involves sorting and making sense of written and narrative data. The goal is not to generalize across a population, but rather to provide understanding and explanation from the respondent's perspective.

DISSEMINATION PLAN

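### The ICIQ-SF and EPIC-UI score regressions adjust for a "baseline" measured after randomisation, so they miss the total programme effect if the programme changes that early score

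*Combined protocol and SAP*

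**What the plan says.** Data Analysis, Outcome Variables Analysis, specifies multiple regression of the 6- and 12-month ICIQ-SF and EPIC-UI totals on treatment group "while controlling for baseline score (first score after catheter removal post-operatively". No second model or sensitivity analysis is given for these totals. The non-parametric fallback under Preliminary Analyses names no method.

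The timing comes from several places:

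- **Randomisation precedes surgery.** The primary analysis leaves out men who "changed their mind and selected another treatment after randomization but before surgery". Stratification and Randomization uses the Gleason score as a surrogate for the "surgical margins that will be necessary to resect the cancer, which will occur after randomization".
- **Access precedes surgery by at least a week.** Under Recruitment Procedures at the VAMC, "if a participant cannot start the telehealth program at least 7 days before surgery, he will be excluded". The Intervention section plans two weeks of core content before the operation.
- **The arms differ in that content.** The Overview says the control programme has "no content on pelvic floor muscle training and bladder control strategies".
- **Catheter removal** is one to two weeks after surgery (Specific Aims).
- **Score schedule.** ICIQ-SF is weekly and EPIC-UI every four weeks (Follow-Up).
- **A pre-operative score exists.** Table 4 marks both instruments at the pre-operative visit, and the recruitment section says: "Consenting participants will then complete the brief baseline assessment in clinic".

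**The concern.** A covariate measured after randomisation can itself be changed by treatment. The plan intends this: Table 1 says the pre-operative part of the programme may lessen post-operative severity. Conditioning on the first post-catheter score then takes out part of the benefit the trial is meant to measure, and the comparison is no longer fully protected by randomisation. The secondary hypothesis is that these scores will be better in the rehabilitation group, which reads most naturally as the effect of the whole programme.

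EPIC-UI is the more exposed score. If its four-week cycle runs from surgery, which is not stated, its first value falls 4 − 2 = 2 to 4 − 1 = 3 weeks after catheter removal and may also follow post-operative training.

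At stake are the estimates and confidence intervals for two severity scores. The primary log-rank test, the 9- and 12-month continence rates and pad use do not use this covariate.

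**Working it through.** **The plan's own figure.** The plan gives no figure for these regressions. Its only sample size is 78 per arm, for the primary test. HR = ln(0.35)/ln(0.55) = 1.756, as stated. With 156 × 0.55 = 85.8 expected events and one-sided 0.05, power is 0.815 by Freedman's formula and 0.832 by Schoenfeld's, in line with the stated 80%. So 78 per arm is used below.

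**Formula.** Write effects as benefits. Let T be the total effect on the late score, d the effect on the first post-catheter score, and b the within-arm slope of late on early score. By least-squares algebra:

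adjusted coefficient = T − b × d

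It equals T only if d = 0 or b = 0.

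**Assumed inputs** (none is in the documents), in SD units of the first score so that they can be read for either instrument: T = 0.5, residual SD 0.8, two-sided 5%, n = 78 per arm with scores, b = 0.3, 0.5 or 0.7.

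- Planned model: SE = 0.8 × √(2/n + d²/(2n − 2)), df 2n − 3
- Unadjusted: SE = √(b² + 0.64) × √(2/n), df 2n − 2
- Power and coverage from the noncentral t distribution

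Example, b = 0.5 and d = 0.2: estimate 0.5 − 0.5 × 0.2 = 0.40; share lost 0.10/0.5 = 20%; SE = 0.8 × √(2/78 + 0.04/154) = 0.129; coverage of T 87.9%; power 0.870.

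| Early benefit d | Share of T lost, b = 0.3 / 0.5 / 0.7 | Coverage of nominal 95% interval for T | Power, planned model |
|---|---|---|---|
| 0 | 0 / 0 / 0% | 95% | 0.972 |
| 0.1 | 6 / 10 / 14% | 94.4 / 93.3 / 91.6% | 0.954 / 0.937 / 0.915 |
| 0.2 | 12 / 20 / 28% | 92.5 / 87.9 / 80.9% | 0.924 / 0.870 / 0.793 |
| 0.4 | 24 / 40 / 56% | 85.1 / 66.9 / 43.3% | 0.824 / 0.626 / 0.387 |

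Unadjusted power is 0.953 / 0.908 / 0.831 whatever d is.

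**Break-even.** The planned model has at least the unadjusted power up to d of about 0.10, 0.15 and 0.17 SD, and lower mean squared error up to about 0.16 SD. With 62 per arm (about 20% missing) the power thresholds are unchanged and the error threshold is 0.17 to 0.18 SD.

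**Simulation** (6,000 trials per setting, b = 0.5, first-score SD 5 points, T = 2.5 points, d = 0, 0.5, 1, 2 points). If the early score acts causally on the late one, the planned model averages 2.50, 2.24, 2.00, 1.50. If the two scores only share an unmeasured cause, it averages 2.51, 2.26, 2.02, 1.50. The unadjusted estimate stays at 2.49 to 2.52. In the second case none of the 2.5 passes through the early score, so the adjusted coefficient is not the direct effect either.

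**A second scaling** (both scores with SD 1, T = 0.40, correlation 0.5) gives planned-model estimates of 0.40, 0.35, 0.30, 0.20 for d = 0, 0.1, 0.2, 0.4. With T = 0 and d = 0.3 the formula gives 0 − 0.5 × 0.3 = −0.15 SD (simulated −0.148), an apparent late harm where the total effect is nil.

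**The case against.** The choice of covariate is understandable. Men with more than two leakage episodes in six months are excluded, so pre-operative scores probably sit near the floor and predict little. The first post-catheter score is informative, and on the figures above it gives the better estimator when the early effect is small. The regressions could also be read as measuring recovery from the initial post-operative level.

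The harm is conditional. The weekly ICIQ-SF score can fall close to catheter removal, the protocol says almost all men have stress leakage early on, and Table 3 puts general information and goals before locating the muscles, so actual exercise before surgery may be short. A large early benefit is less natural there. The worst cell of the table needs an early benefit 80% as large as the late one (0.4/0.5) and the steepest slope.

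The illustration also fixes the residual SD, so the late-score SD rises with the slope (0.85, 0.94, 1.06) and unadjusted power falls for that reason; with the late SD held at 1 it is 0.87 at every slope. With a one-sided 5% test, planned-model power at d = 0.2 would be 0.96, 0.93, 0.87.

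These points limit the size; they do not remove the problem. Near-universal leakage concerns presence, while total scores measure severity, which can still differ between arms. The share lost depends only on b, d and T, and it and the coverage loss are the same for a one-sided test. The precision argument holds only if the early effect is small, which the plan does not show and its rationale does not assume.

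**Conclusion.** The concern holds. The covariate is measured after randomisation and after different programme content has been offered, and it appears in the only model specified for these two totals. If the programme changes the first post-catheter score, the coefficient and its interval do not describe the total programme effect; the gap is slope × early difference, which is part of the early difference rather than all of it. If there is no early effect, nothing is lost and precision is gained.

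The true size cannot be derived from the documents. Under the assumptions shown, the loss runs from nil to 6–14% of the total effect at an early benefit of 0.1 SD, 12–28% at 0.2 SD and 24–56% at 0.4 SD. This should be fixed, but its reach is two of nine listed secondary items. Confidence is high on the structural point; the magnitude is illustrative.

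**What to change.** Make the main model for both totals a regression of the 6- and 12-month score on group, the pre-operative visit score (Table 4) and the randomisation factors, without the first post-catheter score. The factors are age ("Age (<65 years and 65 or older"), Gleason score (below 7, 7 or above) and site, since "Each site will have a separate randomization schedule to avoid unequal distributions between sites".

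State whether the pre-operative score is taken before randomisation. The recruitment section places it before programme access, so programme content should not have altered it, but its order relative to randomisation is not given. If it does not precede randomisation, adjust for the randomisation factors only.

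Report the first post-catheter score by arm as an early outcome. Keep the currently planned model as a supportive analysis, labelled as not estimating the total programme effect.

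The cost is analysis-plan wording; no new data are needed. The downside is precision: with near-floor pre-operative scores the new model may be close to unadjusted. If there is no early effect, power under the same assumptions would be 0.95, 0.91 or 0.83 (slopes 0.3, 0.5, 0.7) instead of 0.97, and with 62 per arm 0.90, 0.83 or 0.74 instead of 0.93.
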